11.1.3 Subgroup Analysis

In order to assess the consistency of treatment benefit with respect to the primary efficacy endpoint, forest plots and summary tables will be provided for the following subgroups:

- Race (White, Black, Other)
- Ethnicity (Hispanic or Latino, Not Hispanic or Latino)
- Sex (Male, Female)
- Number of days since onset of symptoms at time of randomization (<6 days or \geq 6 days)

- Comorbidities and risks consist of the following:
 - Age (<65 years, ≥65 years)
 - Presence of chronic pulmonary disease, COPD, pulmonary hypertension (Yes, No)
 - Diabetes mellitus (type 1 or type 2) requiring medication or insulin (Yes, No)
 - Hypertension, requiring at least 1 oral medication for intervention (Yes, No)
 - Immunocompromised status due to disease or medication (Yes, No)
 - Chronic disease associated with high risk for severe COVID-19 (Yes, No)
 - BMI groups (<35 kg/m², ≥35 kg/m²)

11.2 Secondary Analysis

Secondary analyses will be conducted in the ITT population. Sensitivity analyses of secondary analyses will be performed using the mITT and PP populations, to assess the robustness of the secondary results.

11.2.1 Estimand

The treatment policy estimand with respect to the secondary efficacy objective is defined for the key secondary endpoints by the following:

Population: Participants in the ITT population.

Patient-level outcome: Time to disease resolution through day 28.

Intercurrent events: The following intercurrent events to be taken into account:

1. If a death occurs prior to Day 28, the participant will be considered as not having disease resolution through Day 28 (i.e., censored at Day 28).
2. If a participant is lost to follow-up prior to Day 28, the participant will be considered as not having disease resolution and will be censored at the time of lost to follow-up.
3. If a participant discontinues the study [for any reason: lost to follow-up, progression to moderate or severe COVID-19 (or worse), withdrawal of consent] prior to initiation of IP dosing on Day 1 and no symptoms resolution assessment is available, the participant will be considered as not having disease resolution and will be censored on Day 1.

Participants who discontinue study intervention will be followed at least until end of study, Day 35.

Population-level summary measure: Median time to disease resolution.

11.2.2 Disease Resolution

11.2.2.1 Time to Disease Resolution (Symptoms Resolution)

Disease resolution is defined as symptoms resolution (new onset coronavirus disease 2019 (COVID-19) symptoms resolved, and pre-existing symptoms returned to baseline) through Day 28. For the time to disease resolution analysis, the following hypothesis will be tested: prophylactic treatment with rivaroxaban will increase the rate of time to disease resolution relative to placebo in high risk participants with mild COVID-19.

Time to disease resolution is defined as the time from first dose to the date of symptoms resolution (as determined by the investigator: has the participant’s COVID-19 signs and/or symptoms resolved or returned to baseline). The following rules (Table 3) will be used to define time to disease resolution:

Table 3: Censoring rules for time to disease resolution.

| Situation | Outcome | Date of event/censoring |
|---|----------|--|
| Death for any reason | Censored | Day 28 |
| Discontinued prior to Day 28 without disease resolution | Censored | Date of last disease resolution assessment |
| No disease resolution through Day 28 | Censored | Day 28 |
| Randomized, treated but no post-baseline assessments available | Censored | Day 1 |
| Disease resolution through Day 28 | Event | Initial date of last sequence of consecutive disease resolution. |
| Discontinued prior to Day 28 with disease resolution at last assessment | Event | Initial date of last sequence of consecutive disease resolution. |
| Randomized, not treated | Censored | Date of randomization |

*sequence = a series of one or more disease resolutions with no progression.

Example scenarios are included in Table 4 for reference.

Table 4: Example scenarios for time to time to disease resolution.

| Time point | Day 1 | Day 4 | Day 6 | Day 8 | Day 10 | Day 12 | Day 14 | Day 18 | Day 21 | Day 24 | Day 28 | Endpoint |
|----------------|-------|-------|-------|-------|--------|--------|--------|--------|--------|--------|--------|-----------------------------|
| Participant 1 | N | N | N | N | N | N | N | N | N | N | N | No DR, censored at Day 28 |
| Participant 2 | N | Y | N | N | N | N | Died | | | | | No DR, censored at Day 28 |
| Participant 3 | N | Y | Y | N | N | N | Disc. | | | | | No DR, censored at Day 12 |
| Participant 4 | N | Y | N | N | N | Y | Y | Y | Y | Y | N | DR at Day 12* |
| Participant 5 | N | Y | Y | N | N | Y | Y | Y | Disc. | | | DR at Day 12 |
| Participant 6 | N | N | Y | Y | N | N | Y | Y | Y | Y | Y | DR at Day 14 |
| Participant 7 | N | N | N | N | N | N | N | N | N | N | Y | DR at Day 28 |
| Participant 8 | N | N | N | N | N | Y | Y | Y | Y | N | N | No DR, censored at Day 28** |
| Participant 9 | N | Y | NA | NA | NA | NA | NA | NA | NA | NA | NA | DR at Day 4 |
| Participant 10 | N | NA | NA | NA | NA | NA | NA | NA | NA | NA | NA | No DR, censored at Day 1 |
| Participant 11 | Y | Y | Y | Y | Y | Y | Y | Y | Y | Y | Y | DR at Day 1 |
| Participant 12 | N | Y | N | N | N | Y | Y | N | Disc. | | | No DR, censored at Day 18 |

* Due to consecutive days with disease resolution and followed by a day with no disease resolution as the last assessment.

**Due to consecutive days with no disease resolution occur after days with disease resolution.

DR = disease resolution. N=no; Y=yes. NA=Not available.

For time to disease resolution, a stratified 1-sided log-rank test, stratified by number of days since onset of symptoms at time of randomization (<6 days or ≥6 days), will be used to compare between the study intervention and control. The Kaplan-Meier method will be used to obtain the estimates of medians with the associated 2-sided 95% CIs of time to disease resolution,

computed using Brookmeyer and Crowley method. A stratified Cox proportional hazards model, stratified by number of days since onset of symptoms at time of randomization (<6 days or ≥ 6 days) will be used to estimate the hazard ratio and the corresponding 2-sided 95% CI associated with the rate of disease resolution for the study intervention relative to control.

Due to anticipated heterogeneity in the rate of disease resolution, pre-specified baseline variables, including age and BMI will be included in the model to increase precision. Including time-dependent variables, i.e., log(time)-by-variables interactions, to the model to fit a stratified Cox non-proportional hazards model to assess the proportional hazards assumption. If the coefficients for the time-dependent variables are not statistically different from zero based on a chi-square test with 1 degree of freedom would suggest that proportional hazards assumption is adequate for all variables included in the model.

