## 2. Study Schedule of Procedures

**Table 1: Schedule of Activities**

Visits	Screening (≤5 days of Day 1)	Day 1	Day 4	Day 6	Day 8	Day 10	Day 12	Day 14	Day 18	Day 21	Day 24	Day 28	Day 35
Obtain consent	X												
Demographics, past and current medical history including known pregnancy/lactation status, and medication history	X												
Lab-confirmed SARS-CoV-2 positive diagnostic testing 	X												
Inclusion and exclusion criteria	X												
Concomitant medications	X	X	X	X	X	X	X	X	X	X	X	X	X
Randomization 	X												
Study intervention dose (Day 1 Day 21) and record adherence to dosing		X	X	X	X	X	X	X	X	X			
Clinical status assessment using ordinal scales for Gates MRI and WHO		X	X	X	X	X	X	X	X	X	X	X	X
COVID-19 signs and symptoms, temperature, oxygen saturation		X	X	X	X	X	X	X	X	X	X	X	X
AEs assessment	X	X	X	X	X	X	X	X	X	X	X	X	X
Bleeding events and severity assessment		X	X	X	X	X	X	X	X	X	X	X	X
Self-collection of nasal or oropharynx SARS-CoV-2 sample for diagnostic testing 	(X) 	X	X		X			X		X		X	

Note that visits will preferably take place remotely (refer to [Section 8](#)).

SARS-CoV-2= Severe acute respiratory syndrome coronavirus 2

Gates MRI= Bill & Melinda Gates Medical Research Institute

WHO = World Health Organization

 If there is documented positive SARS-CoV-2 diagnostic testing performed with a sample collected ≤10 days prior to screening, the test does not need to be performed. If no documentation, the potential participant will be asked to collect a nasal or oropharynx swab sample to send for testing.

 If documentation of a previous positive SARS-CoV-2 test is not available and a test is performed at screening, randomization will occur after a positive result is obtained.

 Participant will be asked to collect a sample per kit instructions. Discontinue collection during hospitalization and/or per physician's discretion when two consecutive negative results are available at any time during the study.

Note that an unscheduled visit may be required. Additional collection of a nasal swab sample may be performed based on the clinical judgement of the PI.

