#### COVID-19 Characteristics

3. Documented positive SARS-CoV-2 diagnostic testing with a sample collected  $\leq 10$  days of screening.
4. Symptomatic for COVID-19 for  $\leq 7$  days at time of randomization (symptomatic is defined as having at least one of the following symptoms of COVID-19 that is of new onset or has worsened from baseline: fever, chills, myalgia, arthralgia, headache, fatigue, cough, sore throat, nasal congestion, nausea, vomiting, or diarrhea).

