## **7.2. Withdrawal from the Study**

A participant may withdraw from the study at any time at the participant's request or may be withdrawn at any time for the following reasons:

- At the request of the primary care provider if being in the study is no longer in the best interest of the participant
- Participant is judged by the PI to be at significant risk of failing to comply with the provisions of the protocol as to cause harm to self or seriously interfere with the validity of the study results
- At the discretion of the IRB/IEC or government agencies as part of their duties, PI, or Sponsor.
- The participant progressed to moderate or severe COVID-19 (or worse) prior to initiation of IP dosing on Day 1

If the participant withdraws consent for disclosure of future information, the Sponsor may retain and continue to use any data collected before such withdrawal of consent.

Upon withdrawal from the study, the participant may request destruction of any biological samples taken and not tested, and the PI or designee must document this in the site study records.

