### **9.1. Day 1 (first day of study)**

The study staff conducting the visit will:

- Introduce themselves and their role to the participant and confirm the identity of the participant
- Confirm that the means of contact is adequate to conduct the contact/visit

- Confirm that the supplies and the study IP were received in good condition, review the contents received and instructions.
- Remind the participant not to show the study IP tablets if it is a video enabled contact or describe the tablets detailed appearance to maintain the masking of the study staff.
- Collect information on COVID-19 symptoms and signs
- Assess the Gates MRI and WHO ordinal scales and confirm that participant continues to meet criteria for Scale 2 of Gates MRI COVID-19 Ordinal Scale ([Table 7](#))
- Collect information on AEs (note that AEs will be collected from the time the participant signs the informed consent).
- Collect information on concomitant medications
- Collect information on adherence to study IP and any dosing error (if applicable)
- Ask participant to collect nasal sample, temperature, and oxygen saturation during the encounter (study staff will document temperature and oxygen saturation).
- Inquire about pregnancy, as appropriate.

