**Table 7: Gates MRI COVID-19 Ordinal Scale Clinical Endpoint Definitions**

Scale	Category	Endpoint definition
1	Asymptomatic/symptoms similar to pre-COVID status	
 
• No symptoms and signs AND
 
• No limitation of daily activities
 

2	Mild	
 
• Symptomatic AND
 
• No shortness of breath AND
 
• No hypoxemia (<math>O_2</math> saturation <math>\geq 94\%</math> in ambient air)
 

3	Moderate or severe	
 
• Symptomatic AND
 
• Shortness of breath* OR tachypnea (respiratory rate <math>\geq 20</math> min)* OR hypoxemia (<math><94\%</math> in ambient air)*
 

4	Critically ill	
 
• Symptomatic AND
 
• Receiving high flow oxygen OR non-invasive mechanical ventilation
 

5	Critically ill with invasive mechanical ventilation or extrapulmonary complication	
 
• Symptomatic AND
 
• Receiving invasive mechanical ventilation OR Life threatening or debilitating extrapulmonary complications
 

6	Critically ill with Extra-Corporeal Membrane Oxygenation (ECMO)	
 
• Symptomatic AND
 
• Receiving ECMO
 

7	Death	
 
• Death
 

\*For known COPD participants, moderate or severe category requires worsening of shortness of breath or respiratory rate or oxygen saturation from pre-COVID-19 status

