9.3 Baseline definition

Unless otherwise specified, Baseline is defined as the last non-missing assessment (scheduled or unscheduled) prior to the first dose. In the case where the last non-missing assessment and the first dose coincide (i.e., assessments on Day 1), that assessment will be considered pre-intervention (Baseline).

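### Time to symptom resolution counts a dosed participant who is already resolved at the Day 1 baseline as an event at Day 1, which dilutes the secondary resolution comparison

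*SAP*

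**What the plan says.** - **Entry.** Protocol 5.5.1, criterion 4, limits symptom duration in "days at time of randomization (symptomatic is defined as having at least one of the following symptoms of COVID-19". Symptoms are thus tested at randomization, not at first dose. The schedule in Protocol Table 1 places randomization in the column headed "Screening (≤5 days of Day 1".
- **Day 1 check.** Protocol 9.1 has staff "confirm that participant continues to meet criteria for Scale 2 of Gates MRI COVID-19 Ordinal Scale". A recovered participant belongs to scale 1, "Asymptomatic/symptoms similar to pre-COVID status" (Protocol Table 7).
- **What follows the check.** The only change of disease status that Protocol 7.2 lists as a withdrawal reason is "The participant progressed to moderate or severe COVID-19 (or worse) prior to initiation of IP dosing on Day 1". Recovery is not listed, although 7.2 has general discretion clauses.
- **Baseline.** When the last assessment and the first dose fall together on Day 1, SAP 9.3 says "that assessment will be considered pre-intervention (Baseline".
- **Endpoint.** SAP 11.2.2.1 measures time from first dose. Its Table 3 dates the event at the start of the last unbroken run of resolved visits and does not require that start to lie after baseline. Table 4 gives the worked case "Participant 11 | Y | Y | Y | Y | Y | Y | Y | Y | Y | Y | Y | DR at Day 1".
- **Proportions.** SAP 11.2.3 compares the arms on resolution at any time up to Days 8, 14, 21 and 28, with no lower limit that would exclude Day 1.
- **Populations.** SAP 11.2 uses ITT, with mITT and PP as sensitivity sets. Both of these need disease to be mild at study entry, a term that SAP 7.1 does not define.

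**The concern.** By the SAP's own definition the Day 1 reading is a baseline value. Scoring it as an outcome places events at elapsed time zero, before any tablet could act. Table 4 follows from the wording of Table 3, so it is a stated rule and not a slip in one row.

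These participants enter the stratified log-rank test, the Cox model and the Kaplan-Meier medians as the earliest events in each arm, and they count as successes in the cumulative proportions. They carry no information about rivaroxaban. What is at stake is the size and readability of the symptom-resolution results: a real effect would look smaller, and the reported medians would mix recovery before treatment with recovery during it.

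**Working it through.** **1. The plan's own figure.** The documents give no power, event count or effect size for resolution. The only design figure is 294 per group for the primary endpoint (Protocol 10.1, SAP 9.1.1). With 30% and 19.5%, 1-sided 2.5% and 80% power:

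n = [1.960·√(2·0.2475·0.7525) + 0.842·√(0.30·0.70 + 0.195·0.805)]² / 0.105² = 264; 264/0.9 = 293.3, rounded up to 294.

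It reproduces, and nothing in it depends on how resolution is coded.

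**2. The rules side by side (SAP 11.2.2.1).**

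| Participant | Rule | Result |
|---|---|---|
| Resolved at Day 1 and later, dosed | Table 3 event rule; Table 4, Participant 11 | Event at Day 1, elapsed time 0 |
| Recovered before Day 1, never dosed | Table 3, not treated | Censored at randomization |
| Dosed, no assessment after baseline | Table 3 | Censored at Day 1 |
| Resolved at Day 1, dosed, leaves with no later visit | Fits both the row above and the row for leaving while resolved | Not settled |

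The third row means that Day 1 data alone cannot make an event. The first lets the event rest on the Day 1 reading. The first two rows code the same recovered status in two ways.

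**3. Proportions.** Let r be the share resolved at Day 1, equal in both arms, and let pA and pC be the later resolution probabilities among the rest. Then

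[r + (1−r)pA] − [r + (1−r)pC] = (1−r)(pA − pC).

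Example with an assumed control median of Day 14 and hazard ratio 1.30: by Day 14, pC = 0.50 and pA = 1 − 0.5^1.3 = 0.594, a difference of 9.4 points. It becomes 8.9 (r = 5%), 8.5 (10%) and 7.5 (20%).

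**4. Hazard ratio.** At Day 1 everyone is at risk and the events split evenly between arms. A hazard ratio of 1.30 would put 1.30/2.30 = 57% of them on rivaroxaban, so they pull the estimate toward 1. A simulation assumed exponential times with control mean 12 days, a true hazard ratio of 1.30 among those unresolved, visits on Days 4 to 28, Cox with Efron ties, and 60 runs of 2000 per arm. It gave 1.298 (r = 0), 1.285 (5%), 1.259 (10%) and 1.230 (20%).

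**5. Power at the planned size.** A second simulation assumed 300 per arm, an unstratified log-rank test at 1-sided 0.025, an underlying control median of Day 14 and 1,500 replicates (error about 1 point):

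| r | Power, counted as events | Power, left out | HR, counted | HR, left out |
|---|---|---|---|---|
| 5% | 75% | 79% | 1.30 | 1.33 |
| 10% | 71% | 77% | 1.28 | 1.33 |
| 20% | 63% | 73% | 1.25 | 1.33 |

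These hazard ratios are one-step log-rank estimates, which read 1.32 at r = 0 for a true 1.30, so they should be compared within rows. With no true effect, rejection was between 1.9% and 3.0% under either handling.

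**6. Medians.** Under the same assumptions, the share of controls resolved by the Day 10 visit is 1 − 2^(−9/13) = 0.381. With r = 20% it is 0.20 + 0.80·0.381 = 0.505, so the observed median is Day 10. Without Day 1 events the share reaches exactly 0.50 at Day 14, and the simulated median fell on Day 14 or Day 18 depending on the run.

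**The case against.** **ITT is the declared population.** SAP 11.2.1 names it, and these participants were eligible at randomization. The diluted contrast is the all-randomised answer, not a computational error. That stands, and it is why the all-ITT analysis should be kept. It does not explain why a baseline reading should be an event.

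**The sensitivity sets may already remove these cases.** If study entry means Day 1, mITT and PP drop participants at scale 1 that day. This stands in part: the term is undefined, both sets are analysed by treatment received, and both are only supportive.

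**Restriction is a post-randomisation exclusion.** The tablets have been delivered by Day 1, and Protocol 6.7 accepts that their appearance could reveal the arm and bias subjective assessments. This is a real cost, and the counts by arm must be shown.

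**The number may be small.** Table 4 is illustrative. Five days is the longest gap, and Protocol 3.2.2.1 assumes two days for shipment. Only dosed participants are affected. The investigator's yes/no answer on resolution need not match scale 1, partly because Protocol 9.6 leaves loss of smell and taste out of the symptom endpoint. All of this stands; the share is unknown.

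**The trial has stopped for futility on the primary endpoint.** That lowers the stakes but does not remove them, since the resolution endpoints will still be reported.

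A reader might also infer that the composite with viral clearance has the same defect, because the qualifying swab can be 10 + 5 = 15 days old at Day 1. The documents do not support this. The composite needs two consecutive negative tests, and the scheduled swabs are on Days 1 and 4, so on the schedule it cannot be complete before Day 4, after dosing. Nor does criterion 3 require a positive swab on Day 1; a filter on that result would remove eligible participants.

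**Conclusion.** The point holds for the symptom-only endpoint in the main ITT analysis: a stated rule counts a pre-dose status as an outcome, and Table 3 treats neighbouring cases differently. If Day 1 resolvers are balanced between arms, a hazard ratio of 1.30 falls to about 1.28, 1.26 or 1.23 at shares of 5, 10 or 20%, differences in proportions shrink by the factor 1−r, and both medians shorten. The shares, the resolution times and the true hazard ratio are all assumptions; the documents give none of them. The power figures apply to the planned 300 per arm, not to the smaller set left after early stopping.

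Two further stronger readings should be resisted. The rule does not create false positives: balanced events carry no difference between arms, and simulated rejection under no effect stayed near 2.5%. Nor does it touch the primary endpoint or the sample size. It is a dilution problem in a secondary analysis and should be corrected at that level.

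**What to change.** 1. In SAP 11.2.2.1 and 11.2.3, run the symptom-resolution analyses in randomised participants who are unresolved at the Day 1 baseline, analysed as randomised, with the first possible event after Day 1. Keep the all-ITT version alongside.
2. In the restricted analysis, remove the Day 1 event shown for Participant 11, and state in Table 3 that the event date must be post-baseline.
3. Report the number resolved at Day 1 by arm, from the investigator's resolution question. SAP 10.2 already tabulates Day 1 scale status and each symptom by arm, but not this answer.
4. Define study entry in the mITT and PP populations as Day 1, so that these sets agree with the restricted analysis.
5. The viral-clearance composite takes on only the same symptom-baseline restriction.
6. Protocol 9.1 and 7.2 must be reconciled on what follows when the Day 1 check fails through recovery.

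The cost of items 1 to 5 is SAP wording and one flag from Day 1 data already collected, ideally settled before database lock. The downside is that an unknown number of participants leave the restricted analysis after randomization, though before dosing, under imperfect masking. At r = 20% of the planned 600 this would be 120 people, so the counts by arm and the all-ITT result need to sit beside it.

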#### **Secondary endpoints**

Secondary analyses will primarily be conducted in the ITT population, with sensitivity analyses performed in the mITT and PP populations. Specific details of each analysis will be provided in the SAP.

For time to disease resolution endpoints, a stratified Log-rank test will be used. A stratified Cox PH model will be used to estimate the hazard ratios and corresponding CIs associated with the rate of disease resolution for the study intervention relative to control. Due to anticipated heterogeneity in the rate of disease resolution, pre-specified baseline variables, including age, BMI, and days of symptoms at time of enrollment may be included in the model to increase precision. The appropriateness of the proportional hazard ratio assumption will be assessed.

The proportion of participants who achieve disease resolution at each time point through Day 28 will be summarized by treatment group with 95% exact CIs. Differences in the proportion of participants achieving disease resolution between each intervention and control will be assessed using the stratified Miettinen and Nurminen method to compare the difference between two rates [[Miettinen 1985](#)].

The distributions of the Gates MRI scale score and WHO ordinal score will be summarized by day and treatment group. The overall burden of disease for an individual participant may be calculated as the area under the curve over time. Differences in disease scores will be assessed using a linear model assessing the impact of treatment on disease burden, while controlling for baseline disease burden, age, BMI, and days of symptoms at time of enrollment. Differences in disease severity at key timepoints (e.g., Day 14) will also be assessed using a proportional odds model.

The proportion of hospitalized participants will be summarized by treatment group with 95% exact CIs. The relative risk of hospitalization for patients randomized to each intervention relative to control will be assessed using a stratified analysis for the comparison of two rates.

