### **Exploratory endpoints**

SARS-CoV-2 viral load measures will be assessed using a linear mixed effects model, with fixed effects of time, baseline viral load, age, BMI, and days of symptoms at time of enrollment, and a random effect for participant. The measures may be transformed to satisfy the normality assumption needed for the linear mixed effects model fit. Mean viral concentrations will be summarized by treatment group and compared over time based on the model fit.

Viral sequencing may be used to assess the phylogenetic relationships between SARS-CoV-2 viruses obtained from positive nasal swab samples. Phylogenetic trees will be generated to determine whether participants were part of a transmission cluster.

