10.2 Demographics and Baseline Characteristics

Demographic data and other baseline characteristics will be summarized using descriptive statistics only, for the ITT, and Safety population. The denominators for percentages will be the number of participants in each intervention group with non-missing data available for the variable of interest.

Explicitly the following characteristics will be summarized:

- Age (years)
- Age groups (<65 years, ≥65 years; and 18 to <35 years, 35 to <50 years, 50 to <65 years, 65 to <75 years, ≥75 years)
- Sex (Male, female)
- Race (American Indian or Alaska Native, Asian, Black or African American, Native Hawaiian or Other Pacific Islander, White, Mixed Race, Other, Unknown)
- Ethnicity (Hispanic or Latino, Not Hispanic or Latino, Not Reported, Unknown)
- Weight (kg)
- Height (cm)
- BMI (kg/m²)
- BMI groups (<35 kg/m², ≥35 kg/m²)

BMI (kg/m²) will be calculated using the following formula:

$$BMI = \frac{weight (kg)}{height (m) \times height (m)}$$

- Presence of comorbidities factors at randomization
 - Age (<65 years, ≥65 years)
 - Presence of chronic pulmonary disease, COPD, pulmonary hypertension (Yes, No)
 - Diabetes mellitus (type 1 or type 2) requiring medication or insulin (Yes, No)
 - Hypertension, requiring at least 1 oral medication for intervention (Yes, No)
 - Immunocompromised status due to disease (Yes, No)
 - Immunocompromised status due to medication (Yes, No)
 - Chronic disease associated with high risk for severe COVID-19 (Yes, No)
 - BMI groups (<35 kg/m², ≥35 kg/m²)
- Number of days since onset of symptoms at time of randomization [continuous and categorical: original protocol (<3 days or ≥3 days); protocol amendment 1 (<6 days or ≥6 days); and across both protocol versions (<6 days or ≥6 days)]
- Number of days since onset of symptoms at time of Day 1 [continuous and categorical: (<6 days or ≥6 days), where this is calculated as date of Day 1 – date of onset of symptoms + 1.
- SARS-CoV-2 diagnostic test at Day 1 (Positive, Negative)
- Gates MRI and WHO clinical assessment status at Day 1 (applicable categories)
- Oxygen saturation at Day 1
- COVID-19 signs and symptoms, participants with at least 2 symptoms, 3 symptoms, 4 symptoms, etc. at Day 1. Categories will not be mutually exclusive (i.e., patients having at least 3 symptoms will also be summarized in the at least 2 symptoms category).
- COVID-19 signs and symptoms at Day 1: each symptom (Yes, No)

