11.2.2.2 Time to Disease Resolution (Symptoms Resolution and Viral Clearance)

Time to disease resolution that is defined as both viral clearance (two consecutive negative diagnostic tests) and symptoms resolution (new onset COVID-19 symptoms resolved, and pre-existing symptoms returned to baseline) through Day 28 will be analyzed as similarly to that described for time to disease resolution that is defined as symptoms resolution. Participants who have completed Day 21 visit but not Day 35 visit and did not have two consecutive negative tests at the time of study stop will be censored at the time of their last visit.

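### The Cox model for time to disease resolution omits the Day 1 symptom count; if the count is prognostic, the reported hazard ratio sits closer to 1 and its Wald test has less power

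*SAP*

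**What the plan says.** SAP 11.2.2.1 compares the arms with "a stratified 1-sided log-rank test, stratified by number of days since onset of symptoms at time of randomization" (under 6 days, or 6 days and over). Kaplan-Meier medians describe each arm, and SAP 11.2.1 names the median as the summary measure. The hazard ratio comes from "A stratified Cox proportional hazards model, stratified by number of days since onset of symptoms at time of randomization". Because heterogeneity in the rate of resolution is expected, "pre-specified baseline variables, including age and BMI will be included in the model to increase precision". No other covariate is named. The protocol's sentence on the same model (10.5.1, Secondary endpoints) reads "including age, BMI, and days of symptoms at time of enrollment may be included in the model to increase precision".

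Day 1 symptoms are tabulated as a baseline characteristic in SAP 10.2: "COVID-19 signs and symptoms, participants with at least 2 symptoms, 3 symptoms, 4 symptoms, etc. at Day 1", and also symptom by symptom. For its ordinal-scale scores the protocol planned a linear model "while controlling for baseline disease burden, age, BMI, and days of symptoms at time of enrollment", and for viral load a mixed model "with fixed effects of time, baseline viral load, age, BMI, and days of symptoms at time of enrollment". The composite of symptom resolution and viral clearance (SAP 11.2.2.2) "will be analyzed as similarly to that described for time to disease resolution that is defined as symptoms resolution". Day 1 Ct values are summarised descriptively in SAP 11.3.2.

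**The concern.** A participant counts as resolved only when new symptoms have gone and pre-existing ones are back to their pre-COVID level. Entry needs just one of the 12 symptoms in inclusion criterion 4 (Protocol 5.5.1), so Day 1 counts could vary widely. Someone with many symptoms has more to clear than someone with one. The days-since-onset stratum measures how long the illness has lasted, not how much of it remains. The plan adds covariates to deal with heterogeneity, yet leaves out a recorded variable with an obvious link to the endpoint.

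At stake are the hazard ratio and confidence interval reported for a key secondary endpoint. The primary risk difference is not affected.

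**Working it through.** **Figures in the plan.** The documents give no hazard ratio, event count or power for time to disease resolution, so there is nothing to reproduce for this endpoint. The one sample-size figure is for the primary endpoint and does reproduce: 30% against 19.5%, one-sided 2.5%, 80% power gives 264 per group, and 264/0.9 = 293.3, so 294. It does not bear on this point.

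**Taken from the SAP.** Visit days 4 to 28; 300 per arm, 1:1; two onset strata; age and BMI as covariates; 10% dropout. **Assumed.** A true conditional hazard ratio of 1.30 and every measure of prognostic strength.

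**Model A: the plan's model with and without a symptom term.** Stratified Cox fit with Efron ties, 600 participants, 1,500 runs per row. Further assumptions: control median 12 days; hazard ratio 0.90 per SD of age and 0.95 per SD of BMI; symptom burden independent of both. The last column is the equivalent gain in participants, (ln HR₂/SE₂)² ÷ (ln HR₁/SE₁)² − 1, where 1 is age + BMI and 2 adds symptoms.

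| Assumed HR per SD of symptom burden | HR₁ | HR₂ | SE₁ | SE₂ | Power₁ | Power₂ | Gain |
|---|---|---|---|---|---|---|---|
| 1.0 | 1.300 | 1.300 | 0.0902 | 0.0903 | 83.0% | 83.1% | 0% |
| 0.8 | 1.293 | 1.303 | 0.0904 | 0.0906 | 81.5% | 83.5% | 6% |
| 0.7 | 1.273 | 1.299 | 0.0909 | 0.0911 | 75.5% | 82.1% | 17% |
| 0.6 | 1.257 | 1.297 | 0.0915 | 0.0918 | 69.5% | 81.3% | 28% |
| 0.5 | 1.231 | 1.290 | 0.0923 | 0.0927 | 60.6% | 79.2% | 49% |

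Example, row 0.6: ln 1.297/0.0918 = 2.833; ln 1.257/0.0915 = 2.500; (2.833/2.500)² = 1.28.

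The standard error rises by 0.1% to 0.4% on adjustment. All the gain comes from the larger conditional hazard ratio. At a true hazard ratio of 1 both models estimate 0.99 to 1.00 and reject in 2.0% to 3.2% of runs, against a nominal 2.5%.

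**Model B: symptom counts.** Each symptom clears independently with mean 5 days and person-to-person variation of SD 0, 0.5 or 0.8 on the log scale. Resolution is the last clearance, read at the visit days. There are 300 per arm and 300 runs per setting. The fits compare log(count) in and out, without age, BMI or strata, so they isolate the count.

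- Counts 1 to 9: the squared ratio of mean z values is 1.38, 1.30 and 1.26 at SD 0, 0.5 and 0.8. Power goes from 79% to 88%, 46% to 59% and 31% to 36%.
- Counts 3 to 7: the ratios are 1.10, 1.08 and 1.06.
- At SD 0 with counts 1 to 9, the hazard ratio is 1.26 without the count and 1.32 with it.

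With 300 runs, the Monte Carlo error on a power near 80% is √(0.8 × 0.2/300), about 2 points. Repeat runs moved the gains by several points (up to 44% in one setting), so I quote roughly 25% to 40% and 3% to 10%.

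**Fewer participants.** Enrolment stopped for futility and the size of the final efficacy set is not stated. Assume 400 participants with 81% events, D = 324. Schoenfeld power is Φ(½√D × ln HR − 1.96). At 1.30 this is Φ(9 × 0.2624 − 1.96) = 66%; at 1.257, 54%; at 1.231, 46%. Absolute power falls. With 200 per arm in Model B the relative gain stays similar, at 28% to 32% for counts 1 to 9 and 4% to 9% for counts 3 to 7.

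**Proportionality of the count.** In Model B at SD 0, with q = exp(−t/5), the hazard for k symptoms relative to one is k·q·(1 − q)^(k−1) ÷ [1 − (1 − q)^k]. For k = 9 this is 0.09 at Day 5, 0.77 at Day 14 and 0.99 at Day 28. The count can therefore be far from proportional.

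**The case against.** The other side has a good case. Nothing here contradicts the protocol, whose own list for this model was age, BMI and days of symptoms, all optional. The SAP keeps the first two and makes the third a stratum. The test that decides the hypothesis is the log-rank test, which uses no covariates. The prognostic strength is built into the simulations. Resolution is an investigator's yes/no judgement (SAP 11.2.2.1), not a symptom tally. The protocol's burden and viral-load adjustments belong to other models, and SAP version 2.0 dropped the corresponding burden and Ct models (Appendix 5). That version is dated 11 February 2021, after the committee's futility decision of 3 February, so a covariate added now needs a clear record of who chose it.

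All of this stands, and it limits the point to one estimate. It does not remove the omission: the model exists to absorb heterogeneity and a recorded, plausibly prognostic variable is absent. The open wording of the covariate list is no defence, since an incomplete list is not a full pre-specification.

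Three stronger readings are tempting and are not supported:

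- That precision is lost. The standard error does not fall when the count is added.
- That the planned hazard ratio is biased. It is a more marginal quantity, because hazard ratios are non-collapsible, and the shift vanishes when the true value is 1.
- That the planned test of the endpoint loses power through this omission. The power figures above compare Wald tests from two Cox fits; the log-rank test and medians are the same either way.

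**Conclusion.** The point holds as a modest improvement to a secondary estimate. Two conditions are needed: the Day 1 count must predict resolution beyond onset stratum, age and BMI, and the true hazard ratio must differ from 1. The documents cannot confirm either. Under the assumed strengths, a conditional hazard ratio of 1.30 is reported as 1.29 when the count is weakly prognostic (0.8 per SD, about 2 points of power) and as 1.23 when it is strong (0.5 per SD, about 19 points). How much is gained depends mainly on how widely the counts spread.

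For the composite endpoint the same reasoning covers the symptom part. The case for Day 1 viral level is weaker, because the documents do not say how complete Day 1 Ct is.

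**What to change.** In SAP 11.2.2.1, add the Day 1 count of qualifying COVID-19 symptoms beside age and BMI, and state that the list is complete.

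- Exclude anosmia and ageusia, which Protocol 9.6 leaves out of the symptom endpoint.
- Use a linear or log(count + 1) term. A plain log fails at zero, and SAP Table 4 foresees a participant already resolved on Day 1 (Participant 11).
- Have blinded staff choose the form before database lock, and document that the choice was made blinded after the interim.
- Keep the stratified log-rank test as the governing test and report the adjusted hazard ratio and interval as the estimate. Do not add a second p-value without a stated role.
- If the count fails the SAP's own proportionality check, stratify by count category instead.

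In SAP 11.2.2.2, use the same term. Adding the Day 1 swab result by category, with a class for missing values, is optional.

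The cost is one more model term, minor programming, possible non-proportionality to handle, and the record of the blinded choice. No new data collection is needed for the symptom count.
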